6.2.2 Dosage Adjustments, Delays, Rules for Withholding or Restarting, Permanent Discontinuation

Dose reduction for adverse events is not allowed. However, if during the process of administering talimogene laherparepvec in the clinic, the subject cannot tolerate the full dose due to an injection-related adverse event such as pain, the total volume given should be recorded, and the reason for intolerance should be documented as an adverse event.

If talimogene laherparepvec treatment is delayed by > 1 week, that dose will be deemed to have been missed and the subject will proceed to the next scheduled treatment visit.

If talimogene laherparepvec dosing is delayed by more than 4 weeks from the date of the planned dose (ie, approximately 6 weeks from the previous dose) due to the occurrence of an adverse event that is considered related to talimogene laherparepvec, the subject must be permanently withdrawn from talimogene laherparepvec treatment.

If talimogene laherparepvec dosing is delayed by more than 4 weeks from the date of the planned dose (ie, approximately 6 weeks from the previous dose) for reasons other than treatment-related toxicity, the case must be reviewed by the Amgen medical monitor in conjunction with the investigator to determine if the subject can resume talimogene laherparepvec therapy.

Talimogene laherparepvec will be permanently discontinued if a subject has a DLT during the DLT evaluation period, subject achieved a CR, no injectable lesions, clinically relevant (resulting in clinical deterioration or requiring change of therapy) disease progression beyond 24-weeks of treatment, per modified WHO response criteria (Appendix D), or safety concern (refer to [Section 8.1](#)), **reaches a maximum treatment duration of 48 months, or the drug becomes commercially available in Japan**, whichever occurs first.

For additional information, related special warnings, and precautions for the use of talimogene laherparepvec please refer to the latest version of the talimogene laherparepvec Investigator's Brochure.

6.3 Other Protocol-required Therapies

All other protocol-required therapies including, topical anesthetic or injectable local anesthetic medications used for pretreatment of the talimogene laherparepvec injection site that are commercially available are not provided or reimbursed by Amgen (except if required by local regulation). The investigator will be responsible for obtaining supplies of these protocol-required therapies.

Additional details regarding these protocol-required therapies are provided in the IPIM.

6.4 Concomitant Therapy

Throughout the study, investigators may prescribe any concomitant medications or treatments deemed necessary to provide adequate supportive care except for those listed in [Section 6.8](#).

All prescription and non-prescription concomitant therapies are to be collected in the CRF from informed consent through 30 (+7) days after the last dose of talimogene laherparepvec.

For concomitant therapies collect therapy name, indication, dose, unit, frequency, route, start date, and stop date.

6.5 Other Treatment Procedures

Treatment with talimogene laherparepvec may result in the reduction of tumor burden such that surgical resection of a previously unresected lesion becomes possible.

Investigators may choose to resect lesions which become suitable for resection to render the subject free of macroscopic disease. In the event of a complete response, residual visible cutaneous or subcutaneous index lesions must be documented by representative biopsy to not contain viable tumor. If a subject undergoes resection of the lesion in the event other than CR the procedure should be recorded in the source document and CRF. In these instances, if the response of other lesions is at least PR (if other lesions remain), the response should be designated PR with the date of surgery as the date of response. If no residual disease remains following surgery, this should also be noted in the CRF, the response definition again being PR with the date of surgery as the date of response. If no viable melanoma was found in the surgical

specimen and all other tumor lesions resolved completely (if present), the response definition will be CR with the date of surgery as the date of response.

Local palliative radiation treatment for relief of various symptoms including, but not limited to, bleeding or pain associated with the underlying disease will be permitted at any time during the study. Subjects with local symptoms suggestive of disease progression should be evaluated for tumor response per modified WHO response criteria (see [Appendix D](#)) prior to the administration of palliative radiotherapy. If a subject undergoes local radiation, the investigator or designee should notify the sponsor medical monitor as soon as possible and the treatment should be recorded in the source document and CRF. Best overall response (BOR) determination of such subjects who received palliative radiation should be done based on tumor assessments prior to radiation treatment.

If a subject demonstrates evidence of recurrent or new central nervous system (CNS) metastases, talimogene laherparepvec should be withheld and the investigator or designee should notify the Amgen medical monitor as soon as possible. Subjects may be allowed to remain on treatment after discussion between the Amgen medical monitor and the investigator to determine the appropriateness of treatment resumption provided CNS lesions can be treated with stereotactic radiotherapy (including GammaKnife) or resection and if there is no change in the baseline ECOG performance status. Subjects may be allowed to reinitiate talimogene laherparepvec following treatment of CNS metastases while receiving dexamethasone or a similar corticosteroid at no more than 1.5 mg dexamethasone (or 10 mg prednisone or equivalent) per day. If higher doses of a steroid are used, talimogene laherparepvec must be held until that dose level is reached during the period of steroid tapering.

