- Where biopsy has confirmed no tumor to be present, a measure of 0 x 0 mm should be entered for that tumor and all tumors of which the biopsied tumor is representative and these will be used for assessing the patient's overall response status at each assessment

Subjects who have had a procedure to completely/partially resect a lesion will be evaluated as follows:

The procedure itself and all post-procedure lesion assessments should always be recorded in the CRF. A completely resected lesion should be assigned a default code of 0 mm (for target lesions) or "absent" (for non-target lesions). If the resected lesion contained cancer or pathology results were unknown, the recorded tumor assessments post-procedure may be used for tumor burden calculations, but determination of response will be considered unevaluable (UE) for response except in the case of PD.

Measureable Tumor Assessment/Burden

Baseline Documentation of "Index Lesions"

All baseline evaluations should be performed as close as possible to enrollment and never more than 4 weeks (ie, 28 days) prior to enrollment.

At baseline, up to 10 measurable cutaneous, nodal, or soft tissue lesions will be chosen to measure over the course of therapy. The distribution of these index lesions should be representative of the subject's overall disease status. Index lesions should be selected on the basis of their size (lesions with longest bi-dimensionally perpendicular diameters) and suitability for accurate repeated measurements by imaging techniques (CT, MRI or ultrasound) and/or other method such as clinical exam.

The sum of the products of the longest diameter and the perpendicular diameter (SPD) of all index lesions will be calculated as the baseline total tumor burden.

Baseline Documentation of "Nonindex Lesions"

All other lesions (or sites of disease), including any measurable lesions that were not chosen as index lesions will be identified as nonindex lesions. Nonindex lesions should be recorded and assessed qualitatively over the course of therapy.

Follow-up “Index Lesions”

At each subsequent tumor assessment, the SPD of the index lesions are added together to provide the total tumor burden.

Follow-up “Nonindex Lesions”

Nonindex disease measurements are not required and these lesions should be followed as “present,” “absent,” or in rare cases “unequivocal progression.”

Response Criteria

Evaluation of Objective Response

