Unable to Evaluate (UE):	Any index lesion present at baseline which was not assessed, was unable to be evaluated leading to an inability to determine the status of that particular tumor for that time point, or was resected but on pathological review still contained melanoma.
Not Done (ND)	Radiographic image or clinical measurement were not performed at this time point to evaluate the index lesions

Table 6. Definition of Nonindex Lesion Tumor Response

Complete Response (CR):	Disappearance of all nonindex lesions.
Incomplete Response/Stable Disease (SD):	Persistence of 1 or more nonindex tumor(s).
Disease Progression (PD):	
Unequivocal progression of 1 or more nonindex lesions
 
There are 2 types of PD defined in this protocol:
 
Non-clinically relevant disease progression (PDn): PD in subjects who do not suffer a decline in performance status and/or in the opinion of the investigator do not require alternative therapy. Subjects showing PDn as overall response will be allowed to continue study treatment.
 
Clinically relevant disease progression (PDr): PD that is associated with a decline in performance status and/or in the opinion of the investigator the subject requires alternative therapy. Subjects with PDr will be allowed to remain on study until 24 weeks of therapy unless, in the opinion of the investigator, other treatment is warranted.

Unable to Evaluate (UE):	Any nonindex lesion present at baseline which was not assessed, was unable to be evaluated leading to an inability to determine the status of that particular tumor for that time point, or was resected but on pathological review still contained melanoma.
Not Applicable (NA)	No nonindex lesions were identified at baseline
Not Done (ND)	Radiographic image or clinical measurement were not performed at this time point to evaluate the nonindex lesions

Table 7. Matrix for Determining the Overall Response at Each Assessment Point

Index Lesion Response Including New Lesions	Nonindex Lesion Response	Overall Response
CR	CR	CR
	SD	PR
	PDn	PDn
	PDr	PDr
	NA	CR
	UE/ND	UE
PR	CR/SD	PR
	PDn	PDn
	PDr	PDr
	NA	PR
SD	UE/ND	UE
	CR	SD
	SD	SD
	PDn	PDn
	PDr	PDr
	NA	SD
PDn	UE/ND	UE
	CR/SD/PDn/NA/UE/ND	PDn
	PDr	PDr
PDr	Any	PDr
UE/ND	CR/SD/ NA/UE/ND	UE
	PDn	PDn
	PDr	PDr

Subjects with PDn as overall response will be allowed to continue study treatment.

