4.1 Study Endpoints

4.1.1 Primary Endpoints

- Subject incidence of DLTs
- DRR using modified WHO response criteria by investigators

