4.2 Planned Covariates

The following covariates will be used to examine efficacy and safety in subgroups or in multivariate analyses as appropriate:

- Grouped disease stage at baseline: IIIB-IVM1a vs IVM1b-c
- Line of therapy for current disease: 1st line vs 2nd line or later
- Dose level (Dose 1 vs Dose -1, if applicable)

5. Hypotheses and/or Estimations

No formal statistical hypothesis will be tested for safety endpoints in this trial. Based on the well tolerated safety profile from a global phase 3 study, it is hypothesized that talimogene laherparepvec will be safe and well tolerated in Japanese subjects with unresectable stage IIIB-IVM1c malignant melanoma.

A DRR is hypothesized to be consistent with results from the global phase 3 study ([Andtbacka et al., 2015](#)).

6. Definitions

1-year, 2-year survival

The Kaplan-Meier (K-M) estimate of the proportion of subjects alive at 1 year and 2 years from the first dose, respectively.

Actual Follow-up Time

Actual follow-up time for a subject is calculated from the first dose to the last on-study date (ie, death date, or date last known to be alive for patients still alive).

Baseline

Baseline in general refers to study day 1. The baseline value of a parameter (eg, vital signs, laboratory tests, and tumor measurement) is considered to be the latest value prior to receiving any study drug. If a subject did not receive study drug, then the latest value on or prior to the enrollment date is to be used.

Duration of Response (DOR)

DOR is defined as the time from the date of an initial response (CR or PR) to the earlier of PD or death. Subjects who have not ended their response at the time of analysis will be censored at their last evaluable tumor assessment.

Durable Reponse Rate (DRR)

DRR is the incidence of a durable response defined as an OR of CR or PR per modified WHO response criteria lasting continuously for ≥ 6 months and beginning at any point within 12 months of initiating therapy among a set of subjects analyzed. Subjects with an OR who do not have any follow-up tumor assessments will not be regarded as having a durable response.

Evaluable tumor assessment

An overall visit response other than UE.

Event of Interest (EOI)

MedDRA dictionary preferred terms for each EOI search strategy are defined and maintained by Amgen Safety Medical Coding.

Investigational product (IP)

Investigational product refers to talimogene laherparepvec in this study.

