Objective Response (OR) per modified WHO criteria

Objective response will be assessed based on the response of the index lesions and nonindex lesions, and presence or absence of new lesions. Confirmation of complete or partial response is not required. The overall response is derived from time point response assessments as described in Protocol Tables 5, 6, 7.

Overall Response Rate (ORR)

ORR is defined as the incidence of an OR of CR or PR per modified WHO response criteria among a set of subjects analyzed. Subjects who do not have any follow-up tumor assessments will be regarded as non-responders.

Overall Survival (OS)

OS is defined as the interval from the first dose to the event of death from any cause; otherwise, OS is censored at the date the subject was last known to be alive.

Positive qPCR

By performing qPCR analysis, the talimogene laheparepvec DNA is \geq cutoff in the sample. Details are provided in [Appendix B, Section 12](#).

Potential Follow-Up Time

Potential follow-up time for a subject is calculated from the first dose to the analysis data cutoff date.

Progression Free Survival (PFS)

Progression-free survival (PFS) per modified WHO response criteria is defined as the interval from the first dose to the earlier of PD per modified WHO response criteria or death from any cause; otherwise, PFS is censored at the last evaluable tumor assessment.

Quantifiable qPCR

By performing qPCR analysis, the talimogene laheparepvec DNA is \geq LLOQ in the sample. Details are provided in [Appendix B, Section 12](#).

Study day

Study day is calculated from the first day when investigational product is administered to the subject; mathematically stated as Study day = (visit date – first dose date) + 1.

Study Day 1

Study day 1 is defined as the first day of administration of the investigational product after enrollment. The day prior to Study Day 1 is considered Study Day -1.

Study Week 0

The start of investigational product administration to the subject is study week 0. Study day 1 corresponds to the first day of study week 0.

Time to Response (TTR)

This endpoint will only be calculated for those subjects in the safety analysis set with CR or PR. It is defined as the time from first dose to the date of the first CR or PR.

Treatment period

Study day 1 through 30 days after the last administration of investigational product.

Treatment-emergent Adverse Events (TEAE)

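### Protocol 6.5 and Appendix D give opposite response scores to a resection with tumour in the specimen or unknown pathology, and the SAP does not say how a UE visit counts towards a durable response

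*Protocol*

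**What the plan says.** **Protocol 6.5** covers resection when the subject is not in CR. In one branch, "if the response of other lesions is at least PR (if other lesions remain), the response should be designated PR", dated at surgery. In a second branch no disease remains after surgery, "the response definition again being PR with the date of surgery as the date of response". Neither branch depends on what the pathologist finds. A third branch gives CR dated at surgery if the specimen holds no viable melanoma and every other lesion has resolved.

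**Protocol Appendix D** has its own paragraph on resected lesions. Its condition is "If the resected lesion contained cancer or pathology results were unknown"; post-procedure measurements may then enter tumour burden, but "determination of response will be considered unevaluable (UE) for response except in the case of PD". The UE rows of Tables 5 and 6 repeat this for a lesion that was not assessable "or was resected but on pathological review still contained melanoma". Table 7 carries UE into the overall response unless there is PD.

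**SAP 4.1.1** names the primary efficacy endpoint as "DRR using modified WHO response criteria by investigators". **SAP Section 6** says of objective response: "The overall response is derived from time point response assessments as described in Protocol Tables 5, 6, 7". A durable response must last continuously for at least 6 months "and beginning at any point within 12 months of initiating therapy". The only DRR rule for missing assessments is that a responder with no follow-up assessment is not durable. DOR runs from initial response to PD or death and is otherwise censored at the last evaluable assessment, meaning any visit response other than UE. The SAP contains no text on resection and does not cite Protocol 6.5.

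**The concern.** Two current protocol rules give different scores to one event, and the event feeds a primary endpoint. An investigator who follows 6.5 records a response that surgery produced; one who follows Appendix D records UE. The date differs as well: 6.5 starts the response at surgery, which enters the 12-month window, the 6-month duration, TTR and DOR.

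The second gap is about continuity. Under Appendix D scoring, a subject already in PR who has a tumour-containing lesion removed becomes UE at later visits unless PD occurs. DRR needs a continuous response, and the SAP does not say whether a UE visit ends it, is skipped, or leaves durable status undetermined. Tumour assessments are 12 weeks apart, so 6 months covers only two or three visits and the treatment of a single UE visit can settle the matter.

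**Working it through.** **1. The plan's test.** Inputs from Protocol 10.2.1.2 and 10.4.2: exact binomial, 1-sided 5%, null DRR 2%, n = 18, reject at 2 or more durable responders, alternative 16.3%. The rejection probability at a true rate p is 1 − (1 − p)^18 − 18p(1 − p)^17.

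- p = 0.02: 1 − 0.6951 − 0.2554 = 0.0495. SAP Table 2 gives 5.0%.
- p = 0.163: 0.8169. SAP Table 2 gives 81.7% and the protocol 81%.

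The plan's figures reproduce.

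**2. What one subject does at the boundary.**

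| Durable responders | 1-sided p | Exact 90% CI | Null rejected |
|---|---|---|---|
| 1 of 18 | 0.305 | 0.28% to 23.8% | no |
| 2 of 18 | 0.0495 | 2.01% to 31.0% | yes |
| 3 of 18 | 0.0052 | 4.70% to 37.7% | yes |

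At a true DRR of 16.3%, the chance of exactly 1 or exactly 2 durable responders is 14.2% + 23.6% = 37.8%, so a count next to the boundary is not remote. This is a property of the decision rule, not of resection.

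**3. The two scoring rules side by side (resection outside CR).**

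| Situation | Protocol 6.5 | Appendix D |
|---|---|---|
| Specimen tumour-free, all other lesions resolved | CR at surgery | UE rule does not apply |
| Specimen tumour-free, other lesions at least PR | PR at surgery | UE rule does not apply |
| Specimen contains tumour; others at least PR, or none left | PR at surgery | UE unless PD (paragraph and Tables 5 and 6) |
| Pathology unknown; others at least PR, or none left | PR at surgery | UE unless PD (paragraph; not named in the tables) |

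The conflict is confined to the last two rows.

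**4. Two worked subjects (dates assumed), on the visits of Table 2 footnote h: weeks 11, 23, 35, 47, then every 12 weeks.** The SAP gives no day count for 6 months; 365.25 / 2 / 7 = 26.1 weeks is one reading and 24 weeks another.

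- *Response reached only by surgery.* SD at weeks 11 and 23; surgery at week 30 leaves no disease; the specimen contains melanoma. Under 6.5 this is PR from week 30, inside the 12-month window. Under Appendix D it is UE and there is no objective response. Even under 6.5 it is durable only if later UE visits are allowed to carry it: week 47 gives 17 weeks and week 59 gives 29 weeks.
- *Existing response.* PR at week 11; tumour-containing resection at week 20; UE at weeks 23 and 35; PD at week 47. The SAP's DOR definition gives an event at 47 − 11 = 36 weeks. DRR is durable if UE visits are skipped and not durable if they break the response. The SAP does not say which.

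From a PR first seen at week 11, the planned visits document 12, 24 and 36 weeks. Two intervals span 22 to 26 weeks with the 1-week windows. A tumour-containing resection therefore leaves durable status open until the week 35 visit if 6 months means 24 weeks, or until week 47 if it means 26.1. Extra assessments, which the footnote allows, would shorten this.

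**5. Illustration only.** The documents give no resection rate. Suppose a share s of all subjects were durable solely through the 6.5 rule. Added to a true non-surgical DRR of 2%, s = 1%, 2%, 3% or 5% gives a rejection probability of 10.0%, 16.1%, 22.6% or 36.2% instead of 4.95%. If instead the 16.3% includes them and they are scored UE and not durable, power is 78.6%, 75.1%, 71.2% or 62.0% instead of 81.7%. Nothing in the documents supports any particular s.

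**The case against.** The strongest reply is that the SAP largely settles the scoring. DRR and ORR are defined by the modified WHO criteria, which are Appendix D, and the SAP names Tables 5 to 7, which make a resected lesion that still held melanoma UE. This stands. A reader might infer that the choice between PR and UE would be made after the results are seen; the documents do not support that for a tumour-containing specimen. Unknown pathology is not named in the tables, but it arguably fits their wording on lesions whose status cannot be determined, and the Appendix D paragraph covers it outright. What remains is that the investigator, who assesses response for the primary endpoint, has a contrary instruction in 6.5.

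Second, the DOR definition ends a response only at PD or death, which suggests that UE does not end one. That is a fair analogy, but the DRR definition does not adopt it and adds a requirement of continuity.

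Third, the contrast between 1 and 2 of 18 applies to any classification dispute under this rule. A reversal needs a resection outside CR, tumour or unknown pathology in the specimen, timing that decides durability, and a count at the boundary. Protocol 6.8 also bars scheduling elective surgery during treatment and for at least 30 days afterwards. All of this stands and limits the weight of the point. Against it, 6.5 expressly foresees resection after tumour shrinkage.

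**Conclusion.** The contradiction is real and should be fixed. Protocol 6.5 and Appendix D score a tumour-containing or pathology-unknown resection in opposite ways, and the DRR definition does not say what a UE visit does to a continuous response.

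The size cannot be given, because resection frequency is not in the documents; one subject matters only if the count sits at 1 or 2 of 18. Two further inferences go too far. One is that 6.5 turns every resection outside CR into PR: it does so only when the other lesions are at least PR or nothing remains. The other is that a surgical PR is a durable response in itself: it must start within 12 months and be held for 6 months, and Appendix D scores the later visits UE.

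The visit calculation assumes scheduled assessments only and shows both readings of 6 months.

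**What to change.** 1. Reconcile the response-scoring text of Protocol 6.5 with Appendix D. This concerns scoring only, not whether surgery is done.
2. State in SAP Section 6 that DRR, ORR, TTR and DOR use Appendix D scoring for tumour-containing or pathology-unknown resections. A response first reached only through such a resection is then not an objective response, and the subject stays in the denominator.
3. Add one general UE rule used for both DRR and DOR, with a day count for 6 months. For example: a UE visit from any cause does not by itself end a response; durable status needs a documented CR or PR at least 6 months after the initial response with no PD between; DOR is censored at the last CR or PR before a tumour-containing or pathology-unknown resection. In the second worked subject the last CR or PR is week 11, so the subject is not durable and DOR is censored at week 11: the endpoints agree. One difference is left to settle in words: after UE visits unrelated to resection, a later PD still dates the DOR event, while durable status rests on the last documented CR or PR.
4. Report DRR under 6.5 scoring (PR at surgery, later UE visits not ending it) as a sensitivity analysis.

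Cost: a few sentences in the SAP, and a protocol amendment with IEC/IRB approval for 6.5. Resection pathology must reach the analysis data; 6.5 and Appendix D put the procedure and lesion assessments in the CRF but do not say that pathology is captured. Observed DRR and ORR may be slightly lower. Censoring DOR before surgery leaves out any later PD in those subjects, so they should be listed individually.
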